10. APPENDIX

Appendix 1

Data extraction is by automated routine as detailed below:

Currently, data are extracted by weekly bulk upload. Apollo extracts data using the Apollo automated extraction system. Communication is via a SOAP (Simple Object Access Protocol) web service, no special firewall configuration is needed.

At the point of the data drop the data are filtered and processed through a pseudonymisation package encrypting the NHS number. All data are strongly encrypted by a combination of symmetric and asymmetric encryption algorithms: Triple DES and RSA 1024 before transmission, and utilises public and private key pairs unique to each project.

Pseudonymisation is applied at this stage to allow for backwards identification should there be a need to do so as part of an ethically approved study. However, the application of pseudonymisation at this stage also allows the same algorithm to be applied to additional data sources which may be linked data in future years; for example, enabling the linkage of patients' primary care and hospital data without the need to identify a person in the process of conducting this linkage.

Once the data are extracted, they are transferred using the above methodology to the custom built Data Warehouse located within University of Surrey for analysis in secure networks that meet the NHS Information Governance toolkit level 2 standard. These arrangements may change in the future in accordance with developments in technology.

Appendix 2 Code list of AEs**Project title: Post-authorisation passive enhanced safety surveillance of seasonal influenza vaccines: Pilot study in England– Preferred code list**

If a patient presents with adverse events post-vaccination (up to 7 days after), please code (ideally as a problem) as any of the following please code them into their computerised record

EMA surveillance condition	Read Code (5 Byte)	Read Code (CTV3)	Notes
Respiratory/Miscellaneous			
Conjunctivitis	F4C0.	XE16X	Sticky eyes
Rhinorrhoea	1C83.	XM00h	Runny nose
Nasal congestion	H1y1z	X77Gp	Blocked nose
Epistaxis	R047.	Xa96W	Nose bleed
Coryza	H00..	XE0XI	Common cold
Cough	171..	XM0Ch	
Oropharyngeal pain	1922.	1922.	Sore throat
Hoarseness	1CA2.	1CA2.	Hoarse voice
Wheezing	1737.	XE0qs	
Gastrointestinal			
Decreased appetite	R0300	XM07Y	
Nausea	198..	X75qw	Feeling sick
Vomiting	199..	XE0rA	Being sick
Diarrhoea	19F..	19F2.	
Fever/pyrexia			
Fever	165..	X76DI	
Mild fever (<38.5°C rectal)			Please include level of temperature, to help us classify the fever
Moderate fever (38.6-39.5°C)	2E3..	2E3..	
High fever (>39.5°C)			
Sensitivity/anaphylaxis			
Hypersensitivity reactions	SN52.	Xa5uf	Allergic reaction
Anaphylactic reactions	SN501	X70vr	Other allergic reactions
Facial oedema	16J5.	Xa0ls	Facial swelling
Rash			
Rash	M130.	X50Ge	
Generalised rash	2I14.	XM07J	
General non-specific symptoms			
Irritability	225A.	225A.	
Drowsiness	1B67.	XM06R	
Fatigue	168..	1682.	
Headache	1B1G.	XM0CV	
Neurological			
Bell's palsy	F310.	F310.	
Peripheral tremor	1B22.	XE0rn	Tremor/shaking
Guillain-Barre Syndrome (GBS)	F3700	F3700	
Seizure/ Febrile convulsions	1B64.	XaDbE	
	1B6B.	XM03I	Seizure/ fits
Musculoskeletal			
Muscle aches/ myalgia	N2410	X75rs	
Arthropathy	N037.	X701f	Joint pain
Local Symptoms			
	SP3y4		
Local erythema	SP3y5	X75ty	Local reaction to vaccine
	SP3y6		
	SP3y7		

If a patient hands back an Orange Card with their symptoms – please code these and include the code 9G4.. (Drug reaction notification).

N.B.: In coding these conditions there is no assumption about causation; this can only come from advanced analytics.

Principal Investigator: [name]

Practice Liaison Officer: PPD

Project title: Post-authorisation passive enhanced safety surveillance of seasonal influenza vaccines: Pilot study in England– Preferred code list

If a patient presents with adverse events post-vaccination (up to 7 days after), please code (ideally as a problem) as any of the following please code them into the patients computerised record

EMA surveillance condition	Read Code (5 Byte)	Read Code (CTV3)	Notes
Respiratory/Miscellaneous			
Conjunctivitis	F4C0.	XE16X	Sticky eyes
Rhinorrhoea	1C83.	XM00h	Runny nose
Nasal congestion	H1y1z	X77Gp	Blocked nose
Epistaxis	R047.	Xa96W	Nose bleed
Coryza	H00..	XE0XI	Common cold
Cough	171..	XM0Ch	
Oropharyngeal pain	1922.	1922.	Sore throat
Hoarseness	1CA2.	1CA2.	Hoarse voice
Wheezing	1737.	XE0qs	
Gastrointestinal			
Decreased appetite	R0300	XM07Y	
Nausea	198..	X75qw	Feeling sick
Vomiting	199..	XE0rA	Being sick
Diarrhoea	19F..	19F2.	
Fever/pyrexia			
Fever	165..	X76DI	
Mild fever (<38.5°C rectal)			Please include level of temperature, to help us classify the fever
Moderate fever (38.6-39.5°C)	2E3..	2E3..	
High fever (>39.5°C)			
Sensitivity/anaphylaxis			
Hypersensitivity reactions	SN52.	Xa5uf	Allergic reaction
Anaphylactic reactions	SN501	X70vr	Other allergic reactions
Facial oedema	16J5.	Xa0ls	Facial swelling
Rash			
Rash	M130.	X50Ge	
Generalised rash	2I14.	XM07J	
General non-specific symptoms			
Irritability	225A.	225A.	
Drowsiness	1B67.	XM06R	
Fatigue	168..	1682.	
Headache	1B1G.	XM0CV	
Neurological			
Bell's palsy	F310.	F310.	
Peripheral tremor	1B22.	XE0rn	Tremor/shaking
Guillain-Barre Syndrome (GBS)	F3700	F3700	
Seizure/ Febrile convulsions	1B64.	XaDbE	
	1B6B.	XM03I	Seizure/ fits
Musculoskeletal			
Muscle aches/ myalgia	N2410	X75rs	
Arthropathy	N037.	X701f	Joint pain
Local Symptoms			
	SP3y4		
Local erythema	SP3y5	X75ty	Local reaction to vaccine
	SP3y6		
	SP3y7		

If a patient hands back an Orange Card with their symptoms – please code these and include the code 9G4.. (Drug reaction notification).

N.B.: In coding these conditions there is no assumption about causation; this can only come from advanced analytics.

Principal Investigator: [name]

Practice Liaison Officer: PPD

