5. RESEARCH METHODS

a. Study Design

Study setting and population

Routinely collected primary care data from up to ten GP practices will be extracted, to support passive surveillance. Additionally, this passive surveillance will be enhanced by the use of a card-based ADR reporting system. ADR card will be distributed to patients and upon return entered into the EHR system.

EPI-FLU-055 VS UK study targets to follow vaccinated patients between 01/09/2017 and 30/11/2017.

A customized ADR card will be used, which lists pre-defined categories of AEIs to be reported, similarly to study EPI-FLU-046 (2016/2017 season). A field will also be included to report AEIs not listed as well as a field to indicate that no AEI occurred within the 7 days-time window. Patients will be provided with the ADR cards and asked to complete the ADR cards with any AEIs occurring within 7 days post vaccination and to return the cards to the GP practices not later than 14 days post-vaccination^{vii}.

GP practices ordering mainly GSK's *Fluarix Tetra* vaccine for the 2017/18 season will be contacted to inquire about their interest in participating in this study. This may also include existing research contacts and networks of the University of Surrey. GP practices selection will ensure distributed location across England (in London, a Northern city, and rural settings in the North and South) and that the participating population spans different age strata, different levels of deprivation, different ethnic mix, different brand of computerised medical record systems, and different practice sizes. However, this will be tempered by our need to recruit before the start of the influenza immunisation season.

GP practices will also be included based on their ability to comply with the protocol requirements (e.g., number of subjects registered, IT system used). GP practices will be reimbursed for their involvement in this study, according to the National Institute of Health Research (NIHR) guidelines for industry sponsored studies^{viii}.

Of note, regulatory compliance studies can be registered with the National Institute for Health Research (NIHR) Clinical Research Network (CRN) Portfolio^{viii}. Advice will be sought as to whether this study qualifies.

Inclusion criteria

1. Surveillance is planned to apply to vaccination between 1st September and 30th November 2017

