All data processing and analysis in the study will be conducted within the secure IT environment of the Clinical Informatics Research Group, at the University of Surrey. The information security policies and procedures of the Research Group have been approved by the NHS Digital as meeting Information Governance Toolkit (IGT) standards^{xii}.

The system is continuously being updated and modernized in respect of information processing, security and governance processes. The data are automatically extracted from the network of GP practices using a Simple Object Access Protocol (SOAP) web service, on a weekly basis. Data are uploaded to a secure Microsoft SQL server, and processed into aggregated tables; these are then linked to a pre-defined report structure using business intelligence software (Tableau Software, Inc. Seattle, WA, www.tableau.com), to produce a weekly surveillance report in a timely manner.

Using the EHR system, routine data as well as the content of encoded ADR cards will be extracted using methods that Surrey developed and deploys to extract RCGP RSC surveillance data. Sensitive coded data and free-text data will not be extracted. Only relevant EHR data for this study (e.g. disease or symptom, vaccination status and brand) coded by the GPs or other health professional will

¹ This is also referred to as “3DES”, which is the commonly used name for the triple data encryption algorithm (TDEA, also written Triple DEA) symmetric-key block cipher.

² RSA stands for Rivest, Shamir and Aldeman who founded RSA Laboratories. They created large numbers with only two prime factors, a core component of the encryption process

be extracted^{xiii}. Large volume of research that has come out of UK primary care is based on coded data^{xiv}. The quality of primary care data are such that the expectation will be able to detect frequent AEIs.^{xv}

GP practices will be required to use the relevant Read code for ADR notifications, when recording data from a returned card (Read Code: PPD - Adverse drug reaction notification).

Relevant coded data will be extracted, however these are limited to the administration regime, AEIs and batch number fields of prescribing data.

The following routinely collected patient data will be extracted for the study:

- Demographic information: age, gender, ethnicity, date of registration.
- Seasonal influenza vaccine information: date of administration, brand and batch number when available

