Appendix 3 ADR formVersion 1 – May 15th, 2017

CONFIDENTIAL Card unique number: 0000 0000 0000 0

Enhanced safety surveillance of seasonal influenza (flu) vaccine

Study of possible adverse events following immunisation – this surveillance is designed to capture all adverse events following immunisation. Please report if you get any symptoms following your “flu jab” (influenza vaccination).

1. About you – this information is kept confidential and won't leave your practice

About you* we need contact details, please supply a full address so we can link this to your medical record:

First name _____ Surname _____
 Address _____
 Postcode _____ Telephone: _____ Email _____ @ _____
 Signed _____ Date _____ / _____ /2017

*This personal information is only being collected to link any side effects to your record

2. When you were vaccinated / When was the influenza vaccination given

What date were you vaccinated / was the vaccine given _____ / _____ /2017

Where were you vaccinated: At your GP surgery: Yes No If no, say where: _____

3. If you were not the person vaccinated

Information about the person* Male Female Date of Birth _____ / _____ / _____

First name _____ Surname _____

4. Please report any side-effects/conditions in the 7 days after your flu vaccine

Please look at the list of possible vaccine side-effects on the next page – if the person vaccinated has experienced any adverse events – please tick the relevant box and indicate the severity

Please also mark if the symptoms/possible side effects are still persisting

Please return the card in the envelope provided to your GP – please return by post or in person.

Thank you for your help

5. If you had no side effects in the 7 days after vaccination tick and return

I/the person vaccinated has NOT had any side effects or other symptoms following vaccination:

Please return the card in the envelope provided to your GP – please return by post or in person.

Thank you for your help

Formal study name:

Post-authorisation passive enhanced safety surveillance of seasonal influenza vaccines:

Pilot study in England

GSK study abbreviation:

EPI-FLU 046 VS UK

Collaborating Study Sponsors:

University of Surrey, Guildford UK

GlaxoSmithKline Biologicals

Contact:

[name]

Professor of Primary Care and Clinical Informatics

E-mail: PPD

Telephone: +PPD

PPD

Practice Liaison Officer

E-mail: PPD

Telephone: +PPD

Enhanced safety surveillance of seasonal influenza vaccine

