3.3.2. Adverse Drug Reaction card

In order to facilitate the coding of data using a standardised approach, the 10 enrolled GP practices will also distribute an ADR card to their subjects receiving seasonal influenza vaccine or, as appropriate, to their parent or carer.

Subjects will be instructed to record adverse events (refer to [Annex 3](#)) within 7 days following vaccination and to return the card to their GP practice not later than 14 days post-vaccination. Data recorded on these cards will then be recorded by the GP staff into the subject's EHR. The coding will follow a standardised approach to data recording (refer to [Annex 2](#)) and will include a specific code to indicate that the information is derived from those cards.

Of note, the intent will be to issue cards to all vaccinated patients belonging to the enrolled GP practices, however, considering the UK influenza vaccination plan, some vaccinations are expected to occur outside of the GP settings. These are described as opportunistic vaccination, performed by third parties including pharmacists and thus it cannot be excluded that for some patients, ADR cards will not be distributed. These vaccinations will still be encoded in the EHR and those subjects will be included in the study. The adverse events (AEs) will be captured through the routine data collection process (refer to Section 3.3.1).

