7.3.2. Analyses of primary objectives

The weekly incidence rate (per 100 subjects) of any AEIs within 7 days* post-vaccination period reported via ADR card will be estimated by Vaccine group as follows in the Weekly vaccinated cohorts restricted to subjects who received the ADR card:

- The denominator will be the number of subjects in the Weekly vaccinated cohort for the week of interest who received the ADR card
- The numerator will be the number of subjects from the denominator who reported any AEIs on the ADR card within 7 days following vaccination with the seasonal influenza vaccine

**Day of vaccination plus the following 7 days*

The cumulative incidence rate (per 100 subjects) of any AEIs within 7 days post-vaccination period reported via ADR card will be estimated by Vaccine group as follows in the Cumulative vaccinated cohorts restricted to subjects who received the ADR card:

- The denominator will be the number of subjects in the Cumulative vaccinated cohort up to the week of interest who received the ADR card
- The numerator will be the number of subjects from the denominator who reported any AEIs on the ADR card within 7 days following vaccination with the seasonal influenza vaccine

Similarly, weekly and cumulative incidence rates will be estimated for the following AEIs within 7 days post-vaccination period reported via ADR card:

- Fever/pyrexia
- Fever $>38.5^{\circ}\text{C}$ and $>39.5^{\circ}\text{C}$ (with a temperature measurement recorded in EHR; independent of route of measurement)
- Local symptoms (i.e. local erythema)
- Any and each general non-specific symptom: drowsiness, fatigue, headache, irritability and malaise
- Any and each respiratory AE: conjunctivitis, coryza, cough, epistaxis, hoarseness, nasal congestion, oropharyngeal pain, rhinorrhoea, wheezing
- Any and each gastrointestinal AE: decreased appetite, diarrhea, nausea, vomiting
- Any and each sensitivity/anaphylaxis AE: anaphylactic reactions, facial oedema, hypersensitivity reactions
- Rash
- Any and each musculoskeletal AE: arthropathy, muscle aches / myalgia
- Any and each neurological AE: Bell's palsy, Guillain-Barre syndrome, peripheral tremor, seizure / febrile convulsions

Similarly, weekly and cumulative incidence rates of any SAEs within 7 days post-vaccination period reported via ADR card will also be generated.

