7.3.6.2. Subjects who returned the ADR card

The cumulative incidence rates (per 100 subjects) of each AEIs within the 7 days post-vaccination period reported via ADR card, with 95%CI, will be estimated by Vaccine group for the Cumulative vaccinated cohort Weeks 35-48 restricted to subjects who returned the ADR card:

- The denominator will be the number of subjects in the Cumulative vaccinated cohort Weeks 35-48 who returned the ADR card
- The numerator will be the number of subjects from the denominator who reported the AEI on the ADR card within 7 days following vaccination with the seasonal influenza vaccine

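### The practice coding sheet asks for the card code only when a card comes back with symptoms, so nil returns may go uncoded, understating the return rate and inflating AEI rates among card returners

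*Protocol*

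**What the plan says.** **Coding sheet.** Protocol Appendix 2 prints the sheet twice. Each copy ends with the same instruction: "If a patient hands back an Orange Card with their symptoms", code the symptoms and add 9G4.. (Drug reaction notification). It says nothing about a card returned with no symptoms.

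**Protocol body.** Section 5, under study setting, says: "ADR card will be distributed to patients and upon return entered into the EHR system". Under data extraction, practices must use the Read code for ADR notifications "when recording data from a returned card". Neither sentence depends on symptoms. The code is masked there; its label closely matches that of 9G4.. on the sheet.

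**Card.** Box 5 of the form in Protocol Appendix 3 reads: "If you had no side effects in the 7 days after vaccination tick and return".

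**SAP.** Section 3.3.2 refers to Annex 2 for card coding and says that it "will include a specific code to indicate that the information is derived from those cards". Annex 2 lists AEI codes only and has no card code.

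**Analyses that use card status.**
- Primary (SAP 7.3.2): "The denominator will be the number of subjects in the Weekly vaccinated cohort for the week of interest who received the ADR card".
- Card returners (SAP 7.3.6.2): "The denominator will be the number of subjects in the Cumulative vaccinated cohort Weeks 35-48 who returned the ADR card". The card-based part of SAP 7.3.6.1 is restricted in the same way.
- Compliance (SAP 7.3.1): the percentages who received and who returned a card.

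**The concern.** The analysis data are coded EHR entries, and free text is not extracted (Protocol section 5). A returned card counts as returned only if somebody enters a code for it. The person doing so works from the Appendix 2 sheet, which links the code to symptoms. A card with only box 5 ticked has no symptom to code, and a code labelled as a reaction notification does not obviously fit it.

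Under that reading, a coded return is a return with symptoms. The return rate loses its nil cards, and the returner analysis is conditioned on having something to report.

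That analysis matters because SAP 12.2.4 counts everyone who reports nothing as event-free. The primary rate therefore treats non-returners as having no event, and the returner analysis is the planned check on this. If practices also differ in how they code nil cards, differences between vaccine groups among returners could partly reflect coding habits, because practices choose their own brand.

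**Working it through.** **Inputs**
- Vaccinated subjects: 5,000 (Protocol, sample size consideration; SAP 3.1).
- Return proportion: 50%, the approximate figure for the previous pilot (Protocol 4a).
- Everyone vaccinated receives a card: assumed in steps 1 to 4.
- *a*, the share of returned cards with an AEI: not given. Assumed 10%, with a range of 2% to 40%. At 50% return this is 1% to 20% of recipients.
- *f*, the share of nil cards that are coded: not given. Shown from 0 to 1.

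**Step 1. The plan's own figure.** With *a* = 10%, 2,500 cards come back and 250 carry an AEI. As a share of recipients this is 250/5,000 = 5.0%, which is a row of Protocol Table 1 (95% CI 4.4% to 5.6%, RSE 6.2%). Clopper-Pearson gives 4.41% to 5.64%, and RSE = √(0.95/250) = 6.2%. The row reproduces and is not in dispute.

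**Step 2. Effect of uncoded nil cards.** There are 2,250 nil cards.
- Coded returns = 250 + *f* × 2,250
- Apparent return rate = coded returns / 5,000
- Any-AEI rate among coded returners = 250 / coded returns

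| *f* | Coded returns | Apparent return rate | Any-AEI rate among returners |
|---|---|---|---|
| 1 | 2,500 | 50% | 10.0% |
| 0.75 | 1,937.5 | 38.75% | 12.9% |
| 0.50 | 1,375 | 27.5% | 18.2% |
| 0.25 | 812.5 | 16.25% | 30.8% |
| 0 | 250 | 5% | 100% |

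The unclustered 95% CI for the correct 10.0% is 8.85% to 11.24%, so even the 0.75 row falls outside it.

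**Step 3. Other AEI shares, and single AEIs.** In general the returner rate is *a*/[*a* + *f*(1 − *a*)].
- *a* = 2%, *f* = 0.75: 0.02/0.755 = 2.6%. With *f* = 0.25: 0.02/0.265 = 7.5%.
- *a* = 40%, *f* = 0.75: 0.40/0.85 = 47.1%. With *f* = 0.25: 0.40/0.55 = 72.7%.

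SAP 7.3.6.2 tabulates each AEI separately. Every such rate is multiplied by 1/[*a* + *f*(1 − *a*)]. At *a* = 10% this is 1/0.775 = 1.29 for *f* = 0.75 and 1/0.325 = 3.08 for *f* = 0.25.

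**Step 4. Primary rate.** The numerator is 250 and the denominator is 5,000 recipients. Neither depends on *f*, so the rate is 5.0% in every row.

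**Step 5. Card issue (separate question).** If issue were unrecorded and all vaccinees were used as the denominator, the primary rate would be multiplied by the share issued. At assumed shares of 100%, 80% and 60%, 5.0% becomes 5.0%, 4.0% and 3.0%.

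**The case against.** The best defence is that the main text already covers returned cards. Section 5 asks for the code on returned cards without a symptom condition, and it says that the content of encoded cards will be extracted. The limit "these are limited to the administration regime, AEIs and batch number fields of prescribing data" concerns prescribing data and does not exclude card returns. The sheet is an adverse-event coding aid; it is silent on nil cards and does not forbid coding them. Protocol 4a also reports that return rose to about 50% in the previous pilot once a no-AEI field was added, which suggests that nil cards were counted then.

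This shows that the intention is sound and that complete loss of nil cards is a worst case. It does not remove the conflict. The sheet is what coding staff follow, it is narrower than the body text, and no visible list gives a code for a nil return. How the previous pilot identified nil cards is not stated.

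Two stronger readings are tempting:
- *The primary denominator fails because nil cards are uncoded.* It does not. That denominator is card receipt, and subjects with no report count as event-free (SAP 12.2.4).
- *The study has no record of card issue.* This cannot be asserted. Data-capture flow charts 4 and 5, and the appendices between 3 and 7, are not available here. The SAP also separates recipients from all vaccinees, so treating everyone as a recipient is not its plan.

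Nor is 100% exact even with no nil cards coded. A card with only free-text entries under Other could carry the code without a listed AEI.

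**Conclusion.** The concern holds for returned cards. A printed instruction conflicts with the protocol body, and following it gives a wrong return rate (a tertiary outcome) and wrong card-returner rates (a sensitivity analysis). With 50% return and 10% of returned cards showing an AEI, the any-AEI rate among returners would be about 13% to 31% instead of 10% if 75% down to 25% of nil cards are coded, and near 100% if none are. The 50% comes from the previous pilot; the AEI share and the coding shares are assumptions. If practices code every returned card, there is no bias.

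Card issue is a lesser, open question. Both documents accept that some vaccinees may get no card, and the visible code and extract lists (Protocol section 5, SAP 3.4) name no item recording issue. Because receipt defines the primary denominator, the sponsor needs to answer this, but the documents do not show that the item is missing.

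**What to change.** 1. Reword the Appendix 2 sheet so that the returned-card code is entered for every card handed back, with a distinct code when box 5 is ticked.
2. Add both codes to SAP Annex 2 and to the extract lists in Protocol section 5 and SAP 3.4.
3. In SAP 7.3.1 and 7.3.6.2, define a returned card from those codes. Use the same definition in 7.3.6.1.
4. Confirm whether the flow charts or other appendices provide a card-issue record. If so, list it in SAP 3.4 and define receipt from it in SAP 7.3.1 and 7.3.2. If not, add one or state how unrecorded issue is handled.

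The SAP is dated 11 December 2017, after the vaccination window closed on 30 November. If coding is already complete, the SAP should state what practices actually entered for nil cards. Where these cannot be identified, the return rate and returner analysis should be labelled accordingly.

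Cost: a one-page edit, a small change to the extraction query, and a few seconds of coding per card.
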